9.4 Procedures for Unmasking of Study Medication

This is an open-label study.

10. Administrative Items

This protocol is to be conducted in accordance with the applicable Good Clinical Practice (GCP) regulations and guidelines, eg, the International Conference on Harmonisation (ICH) Guideline on GCP.

10.1 Protection of Human Patients

10.1.1 Compliance with Informed Consent Regulations (US 21 CFR Part 50) and Relevant Country Regulations

Written informed consent is to be obtained from each patient prior to any study-related activities or procedures in the study, and/or from the patient's legally authorized representative.

10.1.2 Compliance With IRB or IEC Regulations

This study is to be conducted in accordance with IRB regulations (US 21 CFR Part 56.103) or applicable IEC regulations. The investigator must obtain approval from a properly constituted IRB/IEC prior to initiating the study and re-approval or review at least annually. Allergan is to be notified immediately if the responsible IRB/IEC has been disqualified or if proceedings leading to disqualification have begun. Copies of all IRB/IEC correspondence with the investigator should be provided to Allergan.

10.1.3 Compliance With Good Clinical Practice

This protocol is to be conducted in accordance with the applicable GCP regulations and guidelines.

10.1.4 Compliance With Electronic Records; Electronic Signatures Regulations (US 21CFR Part 11)

This study is to be conducted in compliance with the regulations on electronic records and electronic signature.

10.2 Changes to the Protocol

The investigator must not implement any deviation from or changes of the protocol without approval by Allergan and prior review and documented approval/favorable opinion from the IRB/IEC of a protocol amendment, except where necessary to eliminate immediate hazards to study patients, or when the changes involve only logistical or administrative aspects of the study (eg, change in monitors, change of telephone numbers).

10.3 Patient Confidentiality

A report of the results of this study may be published or sent to the appropriate health authorities in any country in which the study drug may ultimately be marketed, but the patient's name will not be disclosed in these documents. The patient's name may be disclosed to the Sponsor of the study, Allergan, or the governing health authorities or the FDA if they inspect the study records. Appropriate precautions will be taken to maintain confidentiality of medical records and personal information.

10.3.1 Patient Privacy

Written authorization and other documentation in accordance with the relevant country and local privacy requirements (where applicable) is to be obtained from each patient prior to enrollment into the study, and/or from the patient's legally authorized representative in accordance with the applicable privacy requirements (eg, the Health Insurance Portability and Accountability Act Standards for Privacy of Individually Identifiable Health Information ("HIPAA"), European Union Data Protection Directive 95/46/EC ["EU Directive"]).

In accordance with HIPAA requirements, additional purposes of this study may include publishing of anonymous patient data from the study.

10.4 Documentation

10.4.1 Source Documents

Source documents may include a patient's medical records, hospital charts, clinic charts, the investigator's patient study files, as well as the results of diagnostic tests such as X-rays, laboratory tests, and electrocardiograms. The investigator's copy of the eCRF serves as part of the investigator's record of a patient's study-related data.

The following information should be entered into the patient's medical record:

- Patient's name
- Patient's contact information
- The date that the patient entered the study, patient number, and patient randomization [or medication kit] number
- The study title and/or the protocol number of the study and the name of Allergan

- A statement that informed consent was obtained (including the date). A statement that written authorization or other country and local patient privacy required documentation for this study has been obtained (including the date).
- Dates of all patient visits
- All concurrent medications (List all prescription and non-prescription medications being taken at the time of enrollment. At each subsequent visit, changes to the list of medications should be recorded.)
- Occurrence and status of any adverse events
- Vital signs and general physical examination findings
- The results of pregnancy tests performed by the site
- Copies of the laboratory reports generated by the central laboratory for the analysis of blood and urine samples
- Visual acuity worksheets
- Results of abnormal findings from ophthalmic examination (including slit-lamp biomicroscopy, IOP assessment, and indirect ophthalmoscopy examination)
- SD-OCT imaging files and backup copies of electronic records
- Dilated fundus photography files and backup copies of electronic records
- Fluorescein angiography duplicate and backup copies of the electronic records if a digital system is used
- Procedure notes for the study medication administration procedures must include the following:
 - Date and time the vial is removed from the refrigerator
 - Date and time of the procedure
 - Evaluation of the injection site
 - Location of the injection to the nearest clock hour

- Complications, if any
 - The date the patient exited the study, and a notation as to whether the patient completed the study or reason for discontinuation

Source documentation practices must follow Section 4.0 of ICH E6, Good Clinical Practice: Consolidated Guidance and ALCOA, ie, records must be **A**ttributable, **L**egible, **C**ontemporaneous, **O**riginal and **A**ccurate.

10.4.2 Case Report Form Completion

The investigator is responsible for ensuring that data are properly recorded on each patient's eCRFs and related documents. An investigator who has signed the protocol signature page should personally sign for the eCRFs (as indicated in the case report forms) to ensure that the observations and findings are recorded on the eCRFs correctly and completely. The eCRFs are to be submitted to Allergan in a timely manner at the completion of the study, or as otherwise specified by Allergan and will be maintained in a central data repository.

10.4.3 Study Summary

An investigator's summary will be provided to Allergan within a short time after the completion of the study, or as designated by Allergan. A summary is also to be provided to the responsible IRB/IEC.

10.4.4 Retention of Documentation

All study related correspondence, patient records, consent forms, patient privacy documentation, records of the distribution and use of all investigational products, and copies of eCRFs should be maintained on file.

For countries falling within the scope of the ICH guidelines, the sponsor-specific essential documents should be retained until at least 2 years after the last approval of a marketing application in an ICH region and until there are no pending or contemplated marketing applications in an ICH region or at least 2 years have elapsed since the formal discontinuation of clinical development of the investigational product. These documents should be retained for a longer period, however, if required by the applicable regulatory requirement(s) or if needed by the sponsor.

Allergan requires that it be notified in writing if the investigator wishes to relinquish ownership of the data so that mutually agreed-upon arrangements can be made for transfer of ownership to a suitably qualified, responsible person.

10.5 Labeling, Packaging, and Return or Disposal of Study Medications/Treatments

10.5.1 Labeling/Packaging

Study medication will be packaged, labeled, and supplied by Allergan. All study medications will be identified as an investigational compound and will be labeled with the protocol study number and medication kit number. The label will also specify the storage conditions and state that the study medication is limited to investigational use.

10.5.2 Clinical Supply Inventory

The investigator must keep an accurate accounting of the number of investigational units received from Allergan, dispensed or administered to the patients, and the number of units returned to Allergan during and at the completion of the study. A detailed inventory must be completed for the study medication. The study medication must be dispensed or administered only by an appropriately qualified person to patients in the study. The medication is to be used in accordance with the protocol for patients who are under the direct supervision of an investigator. A unit is defined as a single-dose vial.

10.5.3 Return or Disposal of Study Medications/Treatments and/or Supplies

All clinical study medications/treatments and/or supplies will be returned to Allergan or Allergan designee for destruction. Used syringes and needles must be destroyed per local site procedure.

10.6 Monitoring by the Sponsor

A representative of the sponsor will monitor the study on a periodic basis. The determination of the extent and nature of monitoring will be based on considerations such as the objective, purpose, design, complexity, blinding, size, and endpoints of the study.

Authorized representatives of Allergan or regulatory authority representatives will conduct on-site visits to review, audit and copy study-related documents. These representatives will

meet with the investigator(s) and appropriate staff at mutually convenient times to discuss study-related data and questions.

10.7 Handling of Biological Specimens

Samples of blood and urine for evaluation of hematology, chemistries, and urinalysis will be analyzed at a centralized clinical laboratory with certification from a recognized accreditation agency (eg, College of American Pathology [CAP] or Clinical Laboratory Improvement Amendments [CLIA] certification).

Serum samples obtained will be analyzed for abicipar concentrations (free and total) and anti-drug antibodies (binding and neutralizing) by bioanalytical laboratories using validated methods.

Details about the handling, processing, and shipment of all biological specimens are provided in the procedure manual.

All samples will be returned to Allergan or Allergan designee for destruction. Allergan shall have full ownership rights to any biological specimens/samples derived from the study.

10.8 Publications

Allergan as the sponsor, has proprietary interest in this study. Authorship and manuscript composition will reflect joint cooperation between multiple investigators and sites and Allergan personnel. Authorship will be established prior to the writing of the manuscript. As this study involves multiple centers, no individual publications will be allowed prior to completion of the final report of the multicenter study except as agreed with Allergan.

12.1 Glossary of Abbreviations

Term/Abbreviation	Definition
A/G	albumin/globulin
ALT	alanine aminotransferase
AMD	age-related macular degeneration
AREDS	Age-Related Eye Disease Study
AST	aspartate aminotransferase
BAB	binding antibodies
BCVA	best-corrected visual acuity
BUN	blood urea nitrogen
BLQ	below the lower limit of quantitation
CAP	College of American Pathology
CFR	Code of Federal Regulations
CLIA	Clinical Laboratory Improvement Amendments
C _{max}	peak serum concentration after dosing
CNV	choroidal neovascularization
CRT	central retinal thickness
DA	disc area
DARPin	designed ankyrin repeat protein
DME	diabetic macular edema
eCRF	electronic case report form
ETDRS	Early Treatment of Diabetic Retinopathy Study
EU	European Union
FA	fluorescein angiogram
FDA	Food and Drug Administration
GCP	Good Clinical Practice

GGT	gamma-glutamyl transferase
HbA1c	glycated hemoglobin
HIPAA	Health Insurance Portability and Accountability Act
ICH	International Council on Harmonisation
IEC	independent ethics committee
IOP	intraocular pressure
IRB	institutional review board
LDH	lactate dehydrogenase
LFT	liver function test
MedDRA	Medical Dictionary for Regulatory Activities
mPEG20	maleimide polyethylene glycol of 20 kDa
NAB	neutralizing antibodies
OCT	optical coherence tomography
OU	both eyes
PDT	photodynamic therapy
PEG	polyethylene glycol
PK	pharmacokinetic
PPV	pars plana vitrectomy
RBC	red blood cell
RPE	retinal pigment epithelium
SAP	statistical analysis plan
SD-OCT	spectral-domain optical coherence tomography
SE	study eye
SGOT	serum glutamic oxaloacetic transaminase
SGPT	serum glutamic pyruvic transaminase
TEAE	treatment-emergent adverse event
US	United States

VEGF	vascular endothelial growth factor
VEGF-A	vascular endothelial growth factor-A
WBC	white blood cell
YAG	yttrium aluminum garnet

12.2 Protocol Amendment Summary Amendment 1

Title: Evaluation of Abicipar Pegol in Patients with Neovascular Age Related Macular Degeneration

Protocol 1771-201-008 Amendment 1

Date of Amendment: October 2018

Amendment Summary

This summary includes changes made to Protocol 1771-201-008 (Approved January 2018).

Following is a summary of content-oriented changes that were made to each section of the protocol, and a brief rationale for these changes. Minor editorial and document formatting revisions have not been summarized.

Section	Revision	Rationale
[REDACTED]	[REDACTED]	Administrative change
Section 4.5.2	Revised as follows: “Systemic (eg, oral, intravenous, intramuscular) corticosteroids taken within 5 days prior to any study visit regularly (defined as exposure for 5 or more consecutive days)” ”	Administrative change

Approval Date: 16-Oct-2018

Section	Revision	Rationale
Section 5.6.1	
Section title revised as follows: “Treatment Regimen/Dosage Adjustments/Dose Discontinuation”
 
Text revised as follows: “If the study eye develops a treatment-related adverse event at any time during the study, treatment dose may be temporarily held or discontinued and the reason for dose holding or discontinuation will be recorded on the eCRF.”
 
First bullet point revised as follows: “Intraocular inflammation: may hold or discontinue the dose and exit the patient when the event of intraocular inflammation has been resolved at the investigator’s discretion, eg, if intraocular inflammation is graded as ≥ 2+ as assessed by biomicroscopy in the study eye. For more information, refer to Section 6.3.2.”
	Change made for patient safety
[REDACTED]	[REDACTED]	[REDACTED]
[REDACTED]	[REDACTED]	[REDACTED]

Note: Stricken text was removed and underlined text was added.

Approval Date: 16-Oct-2018

ALLERGAN

Protocol 1771-201-008 Amd 1

[REDACTED]

NCT03539549

Study ID: 1771-201-008

Title: Evaluation of Abicipar Pegol in Patients with Neovascular Age-Related Macular Degeneration

Statistical Analysis Plan Amendment 1 Date: 25 July 2018

Analysis Plan

Evaluation of Abicipar Pegol in Patients with Neovascular Age-Related Macular Degeneration

[figure not shown]
Version 1: 2018-07-25

Protocol Number: Development Phase: Product Name: Study Statistician: Sponsor: 1771-201-008 2 Abicipar Pegol (AGN-150998)

This document is the property of Allergan plc and may not, in full or part, be passed on, reproduced, published, distributed to any person, or submitted to any regulatory authority without the express written permission of Allergan plc.

Table of Contents

1.	Intro	duction	4
	1.1	Primary Study Objectives and Design	4
	1.2	Sample Size	5
	1.3	Database Lock	5
2.	Anal	ysis Populations and Data Conventions	5
	2.1	Analysis Populations	5
	2.2	Analysis Visit Windows	5
	2.3	Data Conventions	6
3.	Disp	osition, Exit Status, and Significant Protocol Deviations	7
	3.1	Disposition and Exit Status	7
	3.2	Significant Protocol Deviations	8
4.	Dem	ographics and Other Baseline Characteristics	8
	4.1	Demographics	8
	4.2	Baseline Characteristics	8
	4.3	Prior Medications/Procedures	8
	4.4	Concomitant Medications/Procedures	9
	4.5	Medical History	10
5.	Effic	acy Assessments and Analyses	10
	5.1	Efficacy Assessments	10
		5.1.1 Best-Corrected Visual Acuity (BCVA)	10
		5.1.2 Central retinal thickness (CRT)	10
	5.2	Efficacy Analyses	
6.	Safe	ty Analyses	12
	6.1	Study Treatment – Exposure and Administration	12
		6.1.1 Exposure to Study Treatments	12
	6.2	Adverse Events	12

List of Tables

Table 2	BCVA Change Categories	12

List of Figures

1. Introduction

This document describes the planned analysis that will be used for study 1771-201-008 clinical study report. This is a multicenter, open-label, 28-week study to evaluate abicipar for safety and treatment effect in patients with neovascular AMD.

1.1 Primary Study Objectives and Design

The primary objective is to evaluate abicipar for safety and treatment effect in patients with neovascular age-related macular degeneration (AMD).

This is a multicenter, open-label, 28-week study. Approximately 100 patients will be enrolled to receive 2 mg abicipar administered at Baseline (Day 1) and Weeks 4, 8, 16, and 24. The summary of the Study Design:

Structure: multicenter, open-label, single-arm study

Duration: 28 weeks

Study Treatment Groups: 2 mg abicipar

Controls: not applicable

Dosage/Dose Regimen: intravitreal injections of 2 mg abicipar administered Baseline (Day 1) and Weeks 4, 8, 16, and 24

Enrollment/Stratification: None

1.2 Sample Size

The study will enroll approximately 100 patients. This sample size is determined empirically and is considered as appropriate for the planned assessments.

1.3 Database Lock

The study database will be locked upon study completion.

2. Analysis Populations and Data Conventions

2.1 Analysis Populations

The safety population, consisting of patients who received at least 1 study treatment, will be used for all analyses.

2.2 Analysis Visit Windows

Analysis visit windows are defined according to study days, which are defined in Table 1.

Visit windows defined in Table 1 will be applied to all by-visit analyses of safety and treatment effect variables. Out-of-window visits (including the exit visit) and unscheduled visits will be reassigned to the visit that the actual study days fall within.

In cases where multiple visits occurred within a single visit window, which resulted in multiple data points for the same window, the last visit with non-missing data will be used for analysis.

2.3 Data Conventions

Unless stated otherwise in specific subsequent sections, data conventions and definitions listed below will be applied to all analyses.

- Day 1 is defined as the day when the patient receives the 1st study treatment Study days = visit date – date of the 1st study treatment + 1
- Study duration for the final DBL = date of the Week 28 visit (or early exit) date of the 1st study treatment + 1
- Unless otherwise specified, baseline data refer to assessments performed at Baseline (Day 1) visit prior to the 1st study treatment. Screening or unscheduled visits prior to Baseline (Day 1) visit will be used for baseline in the absence of pertinent data at the Baseline (Day 1) visit
- Data collected after the 1st administration of any non-study (concomitant/prohibited) ocular anti-VEGF treatment in the study eye will be excluded from all efficacy analyses
- When AE date is partial or missing, the following missing data imputation will be used
 - If AE start date is missing, the start date will be assigned to the 1st day of the month if the day of the month is missing or to January if the month of the year is missing

- If AE stop date is missing, the stop date will be assigned to the last day of the month if the day of the month is missing or to December if the month of the year is missing
- Descriptive statistics include the sample size (N), mean, standard deviation (SD), median, minimum (Min), and maximum (Max) for continuous/ordinal data and the frequency distribution includes sample size (N), frequency count, and percentage for categorical data
- Medical Dictionary of Regulatory Activities (MedDRA) nomenclature will be used to code adverse events, medical procedures, biomicroscopy, and ophthalmoscopy findings
- The Anatomical-Therapeutic-Chemical classification text from World Health Organization (WHO) Drug Dictionary will be used to code all medications for drug class and for drug name
- Whenever applicable, metric systems will be used (eg, kilograms [kg] and centimeters [cm]) and all clinical laboratory data will be presented with the Standard International (SI) units

3. Disposition, Exit Status, and Significant Protocol Deviations

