4.4 Exclusion Criteria

The following are criteria for exclusion from participating in the study:

General Exclusion Criteria

[Redacted text block]

Approval Date: 16-Oct-2018

[Redacted text block]

Ocular Exclusion Criteria (Either Eye)

- 8. Active periocular, ocular, or intraocular infection at baseline (Day 1)

[Redacted text block]

[Redacted text block]

Ocular Exclusion Criteria (Study Eye)

[Redacted text block]

Approval Date: 16-Oct-2018

[Redacted]

[Redacted]

[Redacted]

[Redacted]

[Redacted]

17. Previous or concurrent macular laser treatment

[Redacted]

[Redacted]

[Redacted]

- [Redacted]
- [Redacted]
- [Redacted]

[Redacted]

[Redacted]

Approval Date: 16-Oct-2018

[Redacted]

[Redacted]

- [Redacted]
- [Redacted]
- [Redacted]

- Cataract or refractive surgery (excluding yttrium aluminum garnet [YAG] laser posterior capsulotomy) within the last 3 months prior to baseline (Day 1)

[Redacted]

[Redacted]

[Redacted]

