4.5 Permissible and Prohibited Medications/Treatments

4.5.1 Permissible Medications/Treatments

Therapy considered necessary for the patient’s welfare may be given at the discretion of the investigator. All medications must be recorded in the electronic case report form (eCRF). If the permissibility of a specific medication/treatment is in question, please contact Allergan.

- Non-investigational therapies for the non-study eye are permissible at any time, at the investigator’s discretion
- Corticosteroids administered via intra-nasal, inhaled, intra-articular, or ocular topical routes are permitted during the study
- If cataract surgery is necessary, attempt to schedule cataract surgery ≥ 7 days after the most recent study treatment. Study treatment may be resumed ≥ 14 days after cataract surgery, assuming an absence of surgical-related complications

4.5.1.1 Definition of Females of (Non-)Childbearing Potential and/or Acceptable Contraceptive Methods

For purposes of this study, females will be considered of childbearing potential unless they are naturally postmenopausal or permanently sterilized (ie, hysterectomy). Natural menopause is defined as the permanent cessation of menstrual periods, determined retrospectively after a woman has experienced 12 months of amenorrhea without any other obvious pathological or physiological cause. For women of childbearing potential who may participate in the study, the following methods of contraception, if properly used, are generally considered reliable: hormonal contraceptives (ie, oral, patch, injection, implant), male condom with intravaginal spermicide, diaphragm or cervical cap with spermicide, vaginal contraceptive ring, intrauterine device, surgical sterilization (bilateral tubal ligation, bilateral salpingectomy), vasectomized partner, or sexual abstinence. For male patients who participate in the study, condoms should be used as method of contraception.

The investigator and each patient will determine the appropriate method of contraception for the patient during the participation in the study.

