4.5.2 Prohibited Medications/Treatments

The decision to administer a prohibited medication/treatment is done with the safety of the study patient as the primary consideration. When possible, it is recommended to notify Allergan before the prohibited medication/treatment is administered.

Use of the following medications are prohibited during the study:

- Any periocular injection or intravitreally administered therapy other than study medication in the study eye
- Verteporfin PDT for treatment of neovascular AMD in the study eye
- Systemic (eg, oral, intravenous, intramuscular) corticosteroids taken within 5 days prior to any study visit
- Systemic (eg, intravenous, oral) anti-VEGF medications (eg, bevacizumab, ziv-aflibercept) or VEGF-receptor inhibitor (eg, sunitinib, sorafenib, pazopanib)

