4.2 Baseline Characteristics

Baseline characteristics include height (cm), weight (kg), BMI (kg/m²), iris color, subretinal or intraretinal fluid, intraretinal cysts, pigment epithelial detachments, and smoking status. Ocular characteristics of the study eye at baseline include lens status, study eye as the better-seeing eye (defined as baseline $BCVA_{study-eye} > BCVA_{non-study eye}$), BCVA, CRT, and intraocular pressure. Baseline characteristics will be summarized using descriptive statistics.

4.3 **Prior Medications/Procedures**

Prior medications are defined as those received prior to the first study treatment. For analysis purposes, a medication will be considered as prior medication if it satisfies at least one of the following:

- The start date is prior to Baseline (Day 1), regardless of the stop date;
- The start date is unknown but marked as > 1 year; or
- The stop date is prior to or on Baseline (Day 1), regardless of the start date

For medications with a partial start or stop date where "> 1 year" is not marked for the start date or "ongoing" is not marked for the stop date and the day and/or the month is unknown, comparison to the 1^{st} study treatment date, Baseline (Day 1), will start with the year followed by the month, if applicable, for determination of prior medications. In cases where a full determination cannot be made based on the partial information, the start date will be assigned

to the 1st day of the month if the day of the month is missing or to January if the month of the year is missing; conversely, the stop date will be assigned to the last day of the month if the day of the month is missing or to December if the month is missing. This missing data imputation will only be used to determine whether certain medication is considered as prior medication.

Prior medications will be summarized under each drug class and drug name. A separate analysis for prior ophthalmic medications used in the study eye will be performed based on WHODDE base preferred names.

In addition, ocular anti-VEGF treatment history will be summarized with two categories, treatment-naïve and treatment-experienced. Ocular anti-VEGF treatment includes the following anti-VEGF injections ranibizumab, bevacizumab, pegaptanib, and aflibercept or treatment with a systemic anti-VEGF agent including bevacizumab, and ziv-aflibercept or VEGF-receptor inhibitor such as sunitinib, sorafenib, and pazopanib.

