5.2 Efficacy Analyses

All summary on efficacy variables will be based on observed data and will be presented for the study eye only. Additionally, as part of sensitivity analysis, missing data for BCVA will be imputed using the last observation carried forward (LOCF); additionally, data after the first use of prohibited medications will be also be replaced by LOCF. Efficacy variables include the following:

- Proportion of patients with stable vision (eg, patients who lose fewer than 15 letters in BCVA from baseline)
- Proportion of patients with a gain of 15 or more ETDRS letters in BCVA from baseline
- Proportion of patients with a gain of 10 or more ETDRS letters in BCVA from baseline
- The proportions of patients with BCVA of 70 letters (20/40 Snellen equivalent) or better in the study eye at each post-baseline visit
- Mean change from baseline in BCVA
- Mean change from baseline in CRT as assessed with SD-OCT

For binary response variables (eg, stable vision, 10 or 15 letter gain, and BCVA of 70 letters) the proportion of patients with a response at each post-baseline visit will be calculated. The 95% Confidence Interval (CI) for the proportion will be calculated using the exact method.

For continuous variables, change from baseline in BCVA and in CRT will be summarized by visit with means, medians, standard deviations, minimum, and maximum. The 95% of confidence interval for the mean change will be calculated based on *t*-distribution and presented.

BCVA change from baseline for the study eye at each follow-up visit will be classified into the following 7 categories:

Tab	ole 2	BCVA Change Categories
	Category	Description
	1	\geq 15 letters improvement
	2	\geq 10 and < 15 letters improvement
	3	\geq 5 and < 10 letters improvement
	4	no change (ie, change between +5 and -5 letters)
	5	\geq 5 and < 10 letters worsening
	6	\geq 10 and < 15 letters worsening
	7	\geq 15 letters worsening

The distribution of the 7 categories will be summarized by frequency tabulations based on safety population and observed data.

6. Safety Analyses

The Medical Dictionary for Regulatory Activities (MedDRA) nomenclature will be used to code all adverse events (AEs). The incidence of treatment-emergent AEs (TEAEs, as defined in Section 6.2) will be summarized and presented as the number and percent of patients experiencing the TEAEs during the study period.

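### SAP 2.3 drops efficacy data only after non-study anti-VEGF, so BCVA and CRT after other prohibited study-eye treatments stay in the main summaries, and the handling of macular laser is unclear

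*SAP*

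**What the plan says.** SAP 2.3 (Data Conventions) has one rule that removes efficacy data after another treatment: "Data collected after the 1st administration of any non-study (concomitant/prohibited) ocular anti-VEGF treatment in the study eye will be excluded from all efficacy analyses". The nearest definition of that trigger is in SAP 4.3, written for treatment history: "Ocular anti-VEGF treatment includes the following anti-VEGF injections ranibizumab, bevacizumab, pegaptanib, and aflibercept or treatment with a systemic anti-VEGF agent", followed by VEGF-receptor inhibitors. It contains no laser, PDT or steroid.

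Protocol 4.5.2 introduces its list with "Use of the following medications are prohibited during the study". Two of its four items concern local treatment of the study eye: "Any periocular injection or intravitreally administered therapy other than study medication in the study eye" and "Verteporfin PDT for treatment of neovascular AMD in the study eye". The other two are systemic corticosteroids close to a visit and systemic anti-VEGF or VEGF-receptor inhibitors. No redaction shows inside this list, and macular laser is not on it.

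Macular laser appears in Protocol 4.4 as study-eye exclusion 17: "Previous or concurrent macular laser treatment". Protocol 4.5.1 also has a general permission: "Therapy considered necessary for the patient’s welfare may be given at the discretion of the investigator".

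For the main analysis, SAP 5.2 says: "All summary on efficacy variables will be based on observed data and will be presented for the study eye only". As a sensitivity analysis it imputes missing BCVA by last observation carried forward (LOCF). A further clause, which names no variable, also replaces data after the first prohibited medication by LOCF.

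**The concern.** The SAP accepts that once an eye has received another anti-VEGF agent, its later BCVA and CRT no longer describe abicipar. The same reasoning applies to PDT or a steroid injection in that eye, which the protocol prohibits alongside non-study anti-VEGF injections. The main-analysis rule follows only part of the protocol's own list.

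The design makes this matter. There is one arm and no control, so any change after an added local treatment is read as change on abicipar, with no comparison in which it could cancel. Protocol 4.5.2 foresees that a prohibited treatment may be given for a patient's safety. Neither 4.5.2 nor 8.7 makes exit automatic afterwards, so later visits can be recorded and enter the summaries.

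Macular laser raises a further question. The entry criteria treat it as incompatible with a study eye, but the documents do not settle whether laser given during the study counts as prohibited, or whether any planned analysis would respond to it.

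**Working it through.** **Step 1. Text comparison.** How each study-eye treatment is handled in the visible text:

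| Treatment in the study eye | Protocol status | SAP 2.3 exclusion | SAP 5.2 LOCF, BCVA | SAP 5.2 LOCF, CRT |
|---|---|---|---|---|
| Non-study anti-VEGF injection | Prohibited (4.5.2) | Yes | Yes | Unclear, but already excluded under 2.3 |
| Verteporfin PDT | Prohibited (4.5.2) | No | Yes | Unclear |
| Other periocular or intravitreal injection, such as a steroid | Prohibited (4.5.2) | No | Yes | Unclear |
| Macular laser | Exclusion 17; not in 4.5.2 | No | Uncertain | Uncertain |

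The CRT column is unclear because the SAP 5.2 sentence opens with BCVA and its prohibited-medication clause names no variable. The laser row is uncertain because the trigger is a prohibited medication and laser is not on that list.

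**Step 2. Size for means.** The plan has no figure to reproduce: the sample size of about 100 is empirical, and no frequency of these treatments or effect per eye is given. All inputs below except N are assumptions. If k of N eyes carry an extra effect d from the other treatment, the mean shifts by k × d / N. With N = 100:

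- CRT, k = 1, d = 50 µm: 1 × 50 / 100 = 0.5 µm.
- CRT, k = 5, d = 200 µm: 5 × 200 / 100 = 10 µm.
- BCVA, k = 1, d = 5 letters: 1 × 5 / 100 = 0.05 letter.
- BCVA, k = 5, d = 15 letters: 5 × 15 / 100 = 0.75 letter.

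**Step 3. Size for proportions.** Take k = 5 and assumed observed rates of 90/100 for stable vision and 25/100 for a 15-letter gain, with all 100 patients observed. Intervals, where shown, are exact 95%, as in SAP 5.2.

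| Endpoint and status of the five eyes after the event | Kept as observed | Excluded | Counted as non-responders |
|---|---|---|---|
| Stable vision, all five stable | 90/100 = 90.0% (82.4 to 95.1) | 85/95 = 89.5% (81.5 to 94.8) | 85/100 = 85.0% (76.5 to 91.4) |
| Stable vision, none of the five stable | 90/100 = 90.0% | 90/95 = 94.7% | 90/100 = 90.0% |
| 15-letter gain, all five gain | 25/100 = 25.0% (16.9 to 34.7) | 20/95 = 21.1% (13.4 to 30.6) | 20/100 = 20.0% (12.7 to 29.2) |

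The ceiling is 1 point per patient. It is reached only if every affected eye is a responder after the event and is recounted as a non-responder. Exclusion moves stable vision down by 0.5 point in the first row and up by 4.7 points in the second, so exclusion alone can make results look better.

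**The case against.** The strongest reply is that much of this is already handled. PDT and local steroid injections are on the 4.5.2 list, so the LOCF sensitivity analysis acts on them for BCVA. A reader might infer from SAP 2.3 that no planned analysis deals with these treatments. The documents do not support that: the gap is in the main analysis and, less clearly, in CRT.

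A reader might also infer that macular laser is allowed during the study, because 4.5.2 omits it and 4.5.1 leaves necessary therapy to the investigator. That too goes further than the text. Exclusion 17 covers *concurrent* as well as previous laser, which can be read as barring it during participation. On that reading it would be a deviation, and significant deviations are summarised under SAP 3.2. What stands is that neither reading gives laser a stated consequence in the efficacy analysis.

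Three further points have force:

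- The current drug treatments that Protocol section 1 describes are all anti-VEGF agents, and SAP 2.3 covers that class. Laser, PDT or steroid use may be rare or absent.
- SAP 4.4 gives study-eye concurrent procedures their own summary, so such use would be visible, although no efficacy figure would change.
- The study is descriptive. The visible text states no hypothesis test or success threshold, and the interim analysis focuses on safety. No planned decision is shown to turn on a shift of this size.

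Finally, affected eyes may be those doing poorly, and dropping them favours abicipar, as Step 3 shows. This does not remove the case for a consistent event list, but it means the list needs a second analysis beside it.

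**Conclusion.** The point holds as an inconsistency between the SAP's exclusion rule and the protocol's own list of prohibited study-eye treatments. BCVA and CRT after PDT or a non-anti-VEGF local injection stay in the main observed-data summaries. The sensitivity analysis covers these events for BCVA and leaves CRT unclear. Macular laser may trigger nothing.

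The size is unknown. With an assumed 1 to 5 affected eyes in 100 and 50 to 200 µm per eye, mean CRT change shifts by about 0.5 to 10 µm. A responder proportion shifts by at most 1 point per patient, and by less in many cases. If no such treatment is given, the effect is zero.

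It does not follow that the planned results would favour abicipar: the direction depends on how affected eyes fare after the event, which the documents do not show. This is an inexpensive improvement to the plan and does not call the study into question.

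**What to change.** 1. In SAP 2.3, extend the trigger from ocular anti-VEGF treatment to: ocular anti-VEGF treatment, verteporfin PDT, macular laser, or any other non-study intravitreal or periocular injection in the study eye. Identify events from the concomitant medication and concurrent procedure records.
2. Use the same study-eye list in the SAP 5.2 sensitivity analysis, alongside the prohibited medications that already trigger it, and state that it applies to both BCVA and CRT.
3. Add a sensitivity analysis that counts affected patients as non-responders for the binary BCVA endpoints from the event onward.
4. List the affected patients with treatment, date, and BCVA and CRT before and after.
5. The sponsor should reconcile exclusion 17 with Protocol 4.5.2, so that the status of macular laser during the study is explicit. Which treatments are allowed remains the sponsor's decision.

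The cost is a few lines of SAP text, a short procedure-code list, one extra set of tables and one listing. Concurrent procedures are already to be coded under SAP 4.4. The SAP is dated 25 July 2018 and the current protocol 16 October 2018, so a check against the amended protocol is due in any case. The downside is that a few post-event observations leave the main summary and the remaining eyes may be a favourable selection; item 3 makes that visible for the binary endpoints.
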